3. ECG
4. Body weight
5. Vital signs
6. AE/SAE assessment
7. Urinalysis
8. Blood collection
 - Chemistry panel
 - CBC with differential and platelet count
 - Serum levels of muscle enzymes
 - Serum for exploratory research (including IFN- α assay and proteomics) and storage
 - Serum for autoantibodies (including ANA, anti-SSA, anti-RNP, anti-Jo-1, anti-SRP, anti-Mi-2 antibodies)
 - Whole blood for IFN gene expression analysis
 - Peripheral blood for flow cytometry
 - MEDI-545 serum level
 - Anti-MEDI-545 antibodies
9. Viral surveillance testing
10. Disease activity assessments:
 - MMT
 - Extramuscular activity assessment
 - Pulmonary function tests
 - Physician global activity assessment (included as part of MDAAT)
 - CLINHAQ (includes Patient global activity assessment)
 - Myositis Damage Index
 - SF-36v2
 - WPAI: SHP Questionnaire
 - Pruritus VAS (DM patients only)
 - CDASI (DM patients only)
 - DLQI (DM patients only)
11. Skin photographs (optional, DM patients only, within 7 days of the visit)

Study Days 210, 266, 322 (\pm 7 Days): Follow-Up Period

Visits 18, 20, 22

1. Record concomitant medications
2. Vital signs
3. AE/SAE assessment
4. Viral surveillance testing (Study Day 266 only)
5. Urinalysis includes collection of urine for β HCG (for women who are sexually active and are not surgically sterile or at least 2 years postmenopausal) on Study Day 266 only
6. Blood collection
 - Chemistry panel
 - CBC with differential and platelet count
 - Serum levels of muscle enzymes
 -
 - MEDI-545 serum level

Study Days 238, 294 (\pm 7 Days): Follow-Up Period

Visits 19, 21

1. Record concomitant medications
2. Vital signs
3. AE/SAE assessment
4. Urinalysis
5. Blood collection
 - Chemistry panel
 - CBC with differential and platelet count
 - Serum levels of muscle enzymes
 - Serum for exploratory research (including IFN- α assay and proteomics) and storage
 - Whole blood for IFN gene expression analysis
 - Peripheral blood for flow cytometry
 - MEDI-545 serum level
 - Anti-MEDI-545 antibodies
6. Disease activity assessments:
 - MMT
 - Extramuscular activity assessment
 - Physician global activity assessment (included as part of MDAAT)
 - CLINHAQ (includes Patient global activity assessment)
 - WPAI: SHP Questionnaire
 - Pruritus VAS (DM patients only)
 - CDASI (DM patients only)
 - DLQI (DM patients only)
7. Skin photographs (optional, DM patients only)

Study Day 350 (± 7 days): Final Visit or Discontinuation Visit

If a patient discontinues the study prematurely after Study Day 196 and prior to Study Day 350, he or she should return to the study site and complete the following evaluations. If a particular assessment has been performed within 2 weeks before the discontinuation visit, it need not be repeated.

Visit 23

1. Record concomitant medications
2. Physical examination
3. Body Weight
4. ECG
5. Vital signs
6. AE/SAE assessment
7. Urinalysis includes collection of urine for β HCG (for women who are sexually active and are not surgically sterile or at least 2 years postmenopausal)
8. Blood collection
 - Chemistry panel
 - CBC with differential and platelet count
 - Serum levels of muscle enzymes
 - Serum for exploratory research (including IFN- α assay and proteomics) and storage
 - Serum for autoantibodies (including ANA, anti-SSA, anti-RNP, anti-Jo-1, anti-SRP, anti-Mi-2 antibodies)
 - Whole blood for IFN gene expression analysis
 - Peripheral blood for flow cytometry
 - MEDI-545 serum level
 - Anti-MEDI-545 antibodies
9. Viral Surveillance Testing
10. Disease activity assessments:
 - MMT
 - Extramuscular activity assessment
 - Pulmonary function tests
 - Physician global activity assessment (included as part of MDAAT)
 - CLINHAQ (includes Patient global activity assessment)
 - Myositis Damage Index
 - SF-36v2
 - WPAI: SHP Questionnaire
 - Pruritus VAS (DM patients only)
 - CDASI (DM patients only)
 - DLQI (DM patients only)
11. Skin photographs (optional, DM patients only)

3.6 Patient Evaluation Methods

3.6.1 Routine Laboratory and Clinical Evaluations

Clinical evaluations will be performed during screening and throughout the study as indicated in Table 4 and Table 5. Laboratory tests for serum chemistries, hematology, hepatitis serologies, viral infection, pregnancy and urinalysis with microscopic examination will be performed during screening and during the study by a central CLIA-certified laboratory in the United States. Urine pregnancy tests will be performed in female patients who are not postmenopausal or surgically sterile at the time of screening on Study Day 0, prior to study drug administration on Study Days 14, 28, 42, 56, 70, 84, 98, 112, 126, 140, 154, 168, and 182, and on Study Days 266 and 350 using a licensed test. New clinically significant abnormal laboratory results, which in the opinion of the investigator are related to safety, should be repeated as soon as possible (preferably within 24–48 hours).

Additional studies to be performed include ECGs, and chest x-ray (anterior/posterior and lateral).

3.6.2 Viral Surveillance Testing

HSV-1, HSV-2, EBV, CMV, and HPV will be monitored by virus isolation in tissue culture and/or by molecular assays using PCR amplification as indicated in Table 4 and Table 5. The investigator or qualified designee will collect oropharyngeal swabs for HSV-1 and HSV-2 testing. The patient will provide self collect vaginal swabs for HSV-1, HSV-2, and HPV testing. The vaginal swabs may also be collected by an MD/OBGYN or qualified medical personnel such as an appropriately trained nurse practitioner, if previously approved by the sponsor. In addition, blood samples will be collected and tested for EBV and CMV by PCR molecular-based tests.

3.6.3 Tuberculosis Monitoring

At screening, patients will receive tuberculin skin test. Those who are known to have positive tuberculin skin test should not receive the skin test and should be confirmed by chest x-ray that they have no evidence of active TB. Reading of the tuberculin skin test should be performed 48 to 72 hours after administration by a trained person. A 10 mm cut point will be used to determine tuberculin skin test positivity for those patients not on systemic immunosuppressive medication and a 5 mm cut point will be used for those on systemic immunosuppressive medication. Patients who have latent TB must have completed an appropriate course of anti-TB treatment or be on prophylactic treatment.

3.6.4 Pharmacokinetic, Pharmacodynamic, and Immunogenicity Determinations

All PK and IM laboratory evaluations on samples from North American sites will be performed by MedImmune. MEDI-545 serum concentrations and anti-MEDI-545 antibody detection will be measured by ELISA or ECLA (electrochemiluminescent assay). Sera that are collected may be used for additional PK analyses (MEDI-545 characterization) and MEDI-545 antibody analyses.

3.6.5 Safety Biomarkers

Serum will be collected for assessment of safety biomarkers as described in Table 4. In addition, if a Grade 1 or higher infusion reaction occurs during or after study drug administration, serum for assessment of safety biomarkers will be collected as soon as possible after the event, at 60 minutes after the event, and at discharge (see Section 3.4.4 for details). Safety biomarkers include serum levels of mast cell tryptase, cytokines/chemokines, and IgE antibodies.

3.6.6 Evaluations of Disease Activity

3.6.6.1 Serum Creatine Kinase Normalization

Creatine kinase has been the most useful serum enzyme for the diagnosis and assessment of adult patients with DM or PM. It is the most sensitive enzyme to muscle injury, is at times the only one elevated, and the degree of serum CK elevation is often greater than that seen with other muscle enzymes. As emphasized by Bohan and Peter (Bohan, 1975), trends in serum activity but not single values accurately reflect disease activity in individuals and are useful in the management of these patients. In fact, the trend of the CK has been frequently used in clinical practice to assess response to therapy and is reported in case studies to support evidence of clinical improvement. Preliminary data from MedImmune researchers suggest a correlation between CK values and level of type I IFN gene signature in peripheral blood.

Serum CK will be measured as described in Table 4 and Table 5. The relative normalization of serum CK will be derived from the serum CK ULN and the serum CK levels at baseline (Study Day 0 predose) and at the current visit (eg, Study Day 84) using the following formula:

$$\text{Relative Serum CK Normalization} = \frac{\text{Serum CK on Study Day 0} - \text{Serum CK on Current Visit}}{\text{Serum CK on Study Day 0} - \text{Serum CK ULN}} \times 100\%$$

For example, if the serum CK is 1000 U/L on Study Day 0 and the serum CK on the Current Visit is 500 U/L, then the relative serum CK normalization is 62.5% based on a serum CK ULN of 200 U/L.

$$\frac{1000 \text{ U/L} - 500 \text{ U/L}}{1000 \text{ U/L} - 200 \text{ U/L}} \times 100\% = 62.5\%$$

However, if the serum CK on the Current Visit is less than the serum CK ULN, the relative CK normalization will be 100%.

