3.1.1 Inclusion Criteria

Patients must meet *all* of the following criteria:

1. Male or female adults at least 18 years of age at the time of randomization;
2. Written informed consent obtained from the patient or the patient's legal representative prior to receipt of any study medication or beginning study procedures;
3. Probable or definite PM or DM according to the Bohan and Peter criteria (Bohan, 1975);
4. For patients with PM, documentation of a muscle biopsy result that is consistent with the diagnosis of PM;
5. All patients including those with DM must meet at least two of the following criteria:
 - a. Strength in MMT $\geq 80/150$ but $\leq 125/150$ using the MMT-8 muscle group testing (see Appendix A);
 - b. Patient Global Activity Assessment by visual analog scale (VAS) ≥ 2.0 cm on a 10-cm scale, which is included as part of CLINHAQ (see Appendix B);
 - c. Physician Global Activity Assessment by VAS ≥ 2.0 cm on a 10 cm scale, which is included as part of MDAAT (see Appendix C);
 - d. CLINHAQ (see Appendix B) disability index ≥ 0.25 ;
 - e. Global extramuscular activity assessment ≥ 1.0 cm on a 10-cm VAS scale (this measure is the physician's composite evaluation and is based on assessments of activity scores on the constitutional, cutaneous, skeletal, gastrointestinal, pulmonary and cardiovascular scales of the MDAAT [Appendix C]);
6. Subjects with PM must have an elevation of serum CK or aldolase at a minimum level of $1.3 \times$ upper limit of normal (ULN) or serum CK or aldolase at least 2-fold higher than the patient's own lowest value since diagnosis;
7. Subjects with DM must have either an elevated CK or aldolase as above (per inclusion criterion #6) or other laboratory evidence of active myositis. This could include either abnormal signal on skeletal muscle MRI suggestive of inflammation or an electromyogram demonstrated muscle membrane irritability (e.g., fibrillation potentials, positive sharp waves, complex repetitive discharges) and short duration, small amplitude, polyphasic motor unit action potentials.
8. Patients randomized to Dose Cohorts 1, 2, 3A, and 4 must have median fold overexpression of the top 25 type I IFN-inducible genes of 4-fold or greater in whole blood or muscle at the time of screening; patients randomized to Dose Cohort 3B must have low/undetectable expression of type I IFN-inducible genes;

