5.4.3 Exploratory Endpoints

5.4.3.1 Clinical Activity

The major clinical measures of myositis disease activity will include serum creatine kinase normalization, IMACS core set disease activity measures (physician's global activity assessment, patient global activity assessment, muscle strength assessed by MMT, physical function, muscle-associated enzymes, and extramuscular activity assessment), patients' need for new or increased doses of immunosuppressive therapy, changes in patients' immunosuppressive therapy during the follow-up period, photography of skin lesions, and pulmonary function testing. These assessments will be summarized descriptively by treatment group and time point. A descriptive summary of the number and percent of patients who have reached any of the following: 1) complete CK normalization as indicated by relative normalization of 100% and 2) IMACS-defined response will be presented for placebo and each of the MEDI-545 dose group. The major patient-reported outcomes, including SF-36v2 Health Survey, pruritus VAS, CDASI, DLQI, and WPAI: SHP questionnaire will also be summarized descriptively.

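### Relative CK normalization has no condition on baseline CK, so patients who enter with normal CK count as complete normalizers and a rise past ULN scores above 100%

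*Protocol*

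**What the plan says.** Section 3.6.6.1 sets out the inputs: "The relative normalization of serum CK will be derived from the serum CK ULN and the serum CK levels at baseline (Study Day 0 predose". The remaining input is the CK value from whichever later visit is being scored. The numerator is baseline minus current CK and the denominator is baseline CK minus ULN. The worked example takes 1000 U/L falling to 500 U/L: "then the relative serum CK normalization is 62.5% based on a serum CK ULN of 200 U/L". An override follows: "However, if the serum CK on the Current Visit is less than the serum CK ULN, the relative CK normalization will be 100" per cent.

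Section 5.4.3.1 turns the index into a responder outcome, "complete CK normalization as indicated by relative normalization of 100" per cent, tabulated for placebo and each MEDI-545 dose group. It is one of two responder outcomes listed there; the other is the IMACS-defined response. Section 5.3 analyses efficacy in all randomized patients who receive any study drug.

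Eligibility is in Section 3.1.1. For PM, criterion 6 begins "Subjects with PM must have an elevation of serum CK or aldolase at a minimum level of", with the threshold set at 1.3 × ULN, and adds the alternative "or serum CK or aldolase at least 2-fold higher than the patient's own lowest value since diagnosis". For DM, criterion 7 reads "Subjects with DM must have either an elevated CK or aldolase as above (per inclusion criterion #6) or other laboratory evidence of active myositis", with MRI or EMG findings given as examples.

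**The concern.** The index measures how much of the excess over ULN has been removed. That has meaning only when there is an excess at baseline. Three entry routes allow none: raised aldolase with normal CK (PM or DM), a two-fold rise over the patient's own lowest value with no reference to ULN (PM, and DM through criterion 7), and MRI or EMG evidence (DM). Section 3.2 plans for about 40% to 60% of randomized patients to have DM, so these are not marginal provisions.

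For such patients the rule misbehaves in three ways. The override awards 100% to someone who had nothing to normalize. The negative denominator turns a rise past ULN into a large positive score. A baseline exactly at ULN gives a zero denominator. At stake are the CK responder table, the descriptive summary of the index, and whatever weight the interim reviews of clinical activity (Sections 3.3 and 5.5) place on them.

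**Working it through.** **Inputs.** Formula, override and example ULN of 200 U/L: Section 3.6.6.1. Responder definition: Section 5.4.3.1. Group sizes of 6 active and 2 placebo in each of 5 cohorts: Section 3.4.2, Table 1. The baseline and current CK values below, other than the protocol's own example, are illustrative.

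**Rule.** If current CK < ULN, index = 100%. Otherwise index = (baseline − current)/(baseline − ULN) × 100%.

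**The protocol's own figure.** (1000 − 500)/(1000 − 200) = 500/800 = 62.5%. It reproduces.

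**Same rule, baseline at or below ULN (ULN 200 U/L):**

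| Baseline | Current | Calculation | Index |
|---|---|---|---|
| 150 | 140 | override | 100% |
| 150 | 199 | override | 100%, although CK rose |
| 150 | 250 | (−100)/(−50) | +200% |
| 150 | 300 | (−150)/(−50) | +300% |
| 190 | 400 | (−210)/(−10) | +2100% |
| 200 | 200 or more | denominator 0 | undefined |

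A rise that stays below ULN scores exactly 100% through the override. Only a rise past ULN scores above 100%.

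**Effect of one normal-at-entry patient who stays below ULN on the complete-normalization rate:**

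- Single active cohort of 6: 1/6 = 16.7 points.
- Cohorts 3A and 3B pooled, since both receive 3.0 mg/kg: 1/12 = 8.3 points.
- Pooled placebo, 5 × 2 = 10: 1/10 = 10 points.

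**Same rule when baseline must exceed ULN.** The denominator is always positive and every rise scores negative: baseline 260 to 300 gives (−40)/60 = −66.7%. A score of 100% then means a fall from above ULN to ULN or below. Baselines just above ULN still give extreme values: 210 to 400 gives (−190)/10 = −1900%, and 201 to 250 gives (−49)/1 = −4900%.

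**The case against.** The strongest reply is about weight. CK normalization is an exploratory measure in a Phase 1b safety study. No formal tests are planned (Section 5.1), the sample size does not rest on it (Section 5.2), and dose escalation rests on safety data (Section 4.9). The interim reviews that inform development cover all safety and efficacy endpoints, not CK alone. This stands, and it sets the severity.

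A second reply is that analysis subsets and denominators are usually left to the SAP, which is not at hand. That answers little here, because the protocol itself fixes the formula, the override and the responder definition. A SAP could repair them only by departing from that text.

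Three stronger readings are tempting, and the document does not support them:

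- A reader might infer that the CK response rate reflects the entry mix rather than the drug. The protocol gives no count or proportion of patients with normal baseline CK, and Section 3.6.6.1 describes CK as the most sensitive of the muscle enzymes, so the number could be small.
- A reader might infer that patients whose CK rises past ULN are counted as responders. Section 5.4.3.1 refers to a value of 100% and does not say whether higher values qualify. The sign reversal certainly reaches the continuous summary; it reaches the responder rate only if values above 100% are counted.
- A reader might treat the extreme negative values just above ULN as the same defect. Those have the correct sign. They show an unstable ratio, and the median, minimum and maximum are planned alongside the mean and SD.

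**Conclusion.** The rule is wrong as written for eligible patients with Day 0 CK at or below ULN. Those who stay below ULN are counted as complete normalizers, those who rise past ULN receive a score above 100%, and a baseline equal to ULN leaves the index undefined once current CK is at or above ULN. The first error follows directly from the override and does not depend on how values above 100% are read.

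One patient of the first kind moves the rate by 16.7 points in a 6-patient active group, 8.3 points if 3A and 3B are pooled, and 10 points in a pooled placebo group of 10. These figures assume the planned group sizes without cohort expansion. How many such patients there are is unknown, so the rate is contaminated to an unknown degree. Because the endpoint is exploratory and descriptive, this is a should-fix point.

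**What to change.** In Sections 3.6.6.1 and 5.4.3.1, define relative and complete CK normalization only for patients with Day 0 CK above ULN, and use the number of such patients in each group as the denominator. List patients with baseline CK at or below ULN separately, with the number whose CK becomes abnormal. This removes all three errors.

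Optionally, because the ratio stays unstable for baselines just above ULN, add change from baseline in log(CK/ULN) in all patients as a supporting continuous summary. This is one reasonable choice and is not needed to correct the errors.

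The cost is a short text change in each section, a programming change and a smaller denominator for CK response. No new data are needed.

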3.6.6.2 IMACS Core Set Disease Activity Measures

The IMACS group proposed a core set of outcome measures to assess a clinical improvement in IIM clinical trials (Rider, 2004). The IMACS core set outcome measures includes the following domains:

- 1) Physician Global Activity Assessment
- 2) Patient Global Activity Assessment
- 3) Muscle Strength
- 4) Physical Function

- 5) Muscle-associated Enzymes
- 6) Extramuscular Activity Assessment

Table 6 summarizes the outcome measures for the 6 IMACS core set domains along with their validated methods of assessment. Clinical improvement (ie, IMACS-defined response) in myositis activity will be determined if 3 of the 6 core set measures improve by $\geq 20\%$, with no more than 2 worsening by $\geq 25\%$ (excluding MMT).

Physician Global Activity Assessment is included as part of MDAAT, and Patient Global Activity Assessment is included as a part of CLINHAQ. In this study, the score for Patient Global Activity Assessment will be extracted from CLINHAQ, so that this indicator is measured only once at each time point.

Table 6 Myositis Core Set of Measures

IMACS Core Set Domain	Validated Method of Assessment
Physician Global Activity Assessment	Horizontal 10 cm VAS as part of MDAAT
Patient Global Activity Assessment	Horizontal VAS of 0 to 10 units as part of CLINHAQ
Muscle Strength	MMT including proximal, distal, and axial muscles assessed on 0-10 or expanded 0-5 point scale
Physical Function	CLINHAQ (Fries, 1980) to measure patient-reported functional status
Serum Muscle-associated Enzymes	At least 2 of CK, LDH ^a , ALT, AST, or aldolase
Extramuscular Activity Assessment	Horizontal VAS of physician’s composite evaluation based on assessments of activity scores on the constitutional, cutaneous, skeletal, gastrointestinal, pulmonary, and cardiovascular scales of MDAAT

a. For LDH, the median percentage change to define clinical improvement is 25%.

3.6.6.3 Pulmonary Function Tests

Patients’ pulmonary function will be tested as a part of the extramuscular portion of MDAAT assessments. Testing will be performed according to ATS/ERS guidelines (Miller, 2005). Prior to testing, patients will be required to withhold short-acting β 2-agonists for at least 6 hours if possible.

3.6.6.4 Criteria for Disease Worsening

Disease worsening is defined as any of the following:

1. Worsening of the patient’s global condition, as assessed by the physician, by ≥ 2 cm on a 10 cm VAS and worsening of muscle strength in MMT by $\geq 20\%$;
2. Worsening of global extramuscular activity assessment (an overall assessment of disease activity in extramuscular systems including constitutional, cutaneous, skeletal, gastrointestinal, pulmonary, and cardiovascular activity) by ≥ 2 cm on a 10-cm VAS; or
3. Worsening of any 3 of 6 IMACS core set activity measures by $\geq 30\%$.

3.6.6.5 Myositis Damage Index

The myositis damage index is a comprehensive tool to assess the extent and severity of damage developing in different organs and systems (Appendix D). The index is composed of two portions. One portion counts the items of damage developing in different organs systems. The other portion, the myositis damage score, consists of a series of 10 cm VAS to quantitate the severity of damage in the same organ system.

3.6.6.6 Patient-Reported Outcomes

In addition to the Patient Global Activity Assessment and CLINHAQ evaluated as part of IMACS core set domains, the following patient-reported indicators will be evaluated: SF-36v2 Health Survey (Appendix E), WPAI: SHP questionnaire version 2.0 (Appendix F), pruritus VAS, CDASI (Appendix G), and DLQI (Appendix H). Pruritus VAS, CDASI, and DLQI will be performed in DM patients only.

SF-36v2 Health Survey is a validated instrument for measuring a person's general health status (Ware, 1992) over the past 4 weeks. It consists of two overall summary scores of physical component summary and mental component summary with eight domains: Physical Function, Role Limitations-Physical, Vitality, General Health Perceptions, Bodily Pain, Social Function, Role Limitations-Emotional, and Mental Health. Scores are calculated as from 0-100, in which higher scores indicate better health.

The WPAI: SHP (Reilly, 1993) consists of 6 items and measures work and activity impairment (including absenteeism, presenteeism, and impairment) over the past 7 days. Responses are expressed as impairment percentages (0-100), in which higher numbers indicate greater impairment, lower productivity, or less favorable outcomes.

Pruritus is an important treatable factor that significantly impacts quality of life for patients with DM (Hundley, 2006). A horizontal 10 cm VAS will be used to measure the severity of itching at a specific point in time. The patient-reported score ranges from 0 (no itching) to 10 (severe itching) (Ortonne, 2005).

Quain (2007) reported that the CDASI (Cutaneous DM Disease Area & Severity Index) scores are normally distributed, display greater reliability than the Cutaneous Assessment Tool, and correlate better with physician than patient global skin measures. This report suggested that the CDASI may be the optimal outcome measure for studies of cutaneous DM. The CDASI is scored from 0-76, in which higher scores indicate greater disease severity.

The DLQI (Findlay, 1994) consists of 10 questions related to symptoms and feelings, daily activities, leisure, work or school, personal relationships, and treatment over the past 7 days. Responses range from 0 (not at all) to 3 (very much) for a range of 0 to 30 with higher scores corresponding to greater impairment in quality of life. The DLQI exhibits good test-retest reliability and has been used extensively in clinical research worldwide (Lewis, 2004). Quality of life impairment in DM, as assessed using the DLQI, is greater than in other skin conditions including psoriasis and atopic dermatitis (Hundley, 2006).

